13.6.2.1. Handling of Missing and Partial Dates

Element	Reporting Detail
General	
 • Partial dates will be displayed as captured in subject listing displays.
Adverse Events	
 • The eCRF allows for the possibility of partial dates (i.e., only month and year) to be recorded for AE start and end dates; that is, the day of the month may be missing. In such a case, the following conventions will be applied for calculating the time to onset and the duration of the event: 
 • Missing Start Day: First of the month will be used unless this is before the start date of study treatment; in this case the study treatment start date will be used and hence the event is considered On-treatment as per Appendix 3: Study Phases and Treatment Emergent Adverse Events. • Missing Stop Day: Last day of the month will be used, unless this is after the stop date of study treatment; in this case the study treatment stop date will be used. • Completely missing start or end dates will remain missing, with no imputation applied. Consequently, time to onset and duration of such events will be missing.

Element	Reporting Detail
Concomitant Medications/Medical History	
 • Partial dates for any concomitant medications recorded in the CRF will be imputed using the following convention: 
 • If the partial date is a start date, a '01' will be used for the day and 'Jan' will be used for the month • If the partial date is a stop date, a '28/29/30/31' will be used for the day (dependent on the month and year) and 'Dec' will be used for the month. • The recorded partial date will be displayed in listings.
Age	
 • The eCRF collects year of birth only. Day and Month will be imputed by Data Management using a PPD for the day and PPD for the month • Age will then be derived referenced to the Screening Date • A footnote to say that age has been imputed will be included in any outputs containing age.

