13.3. Appendix 3: Study Phases and Treatment Emergent Adverse Events

13.3.1. Study Periods

13.3.1.1. 12-Week Treatment Period

The 12-Week Treatment Period is assigned from Study Day 1 to Study Day 84.

13.3.1.2. 12-Week Follow-Up Period

The 12-Week Follow-up Period is assigned from Study Day 85 to Study Day 168.

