13.3.3. Treatment Emergent Flag for Adverse Events

Flag	Definition
Treatment Emergent	
 If AE onset date is on or after treatment start date & on or before treatment stop date plus 10 days.

NOTES:

- If the study treatment stop date is missing, then the AE will be considered to be On-Treatment.
- Time of study treatment dosing and start/stop time of AEs should be considered, if collected.

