13.11.8. Safety Tables

Safety: Tables					
No.	Population	IDSL / Example Shell	Title	Programming Notes	Deliverable [Priority]
Adverse Events (AEs)					
3.1.	Safety	AE1	Summary of Treatment Emergent Adverse Events by System Organ Class and Preferred Term		EOT, SAC
3.2.	Safety	AE1	Summary of Post-Treatment Adverse Events by System Organ Class and Preferred Term		SAC
3.3.	Safety	AE3	Summary of Common (>=5%) Treatment Emergent Adverse Events by Overall Frequency		EOT, SAC
3.4.	Safety	AE1	Summary of Drug-Related Treatment Emergent Adverse Events by System Organ Class and Preferred Term		EOT, SAC
3.5.	Safety	AE15	Summary of Common (>=5%) Non-serious Treatment Emergent Adverse Events by System Organ Class and Preferred Term (Number of Participant and Occurrences)		SAC
3.6.	Safety	AE5A	Summary of All Adverse Events by Maximum Intensity by System Organ Class and Preferred Term		SAC

Safety: Tables					
No.	Population	IDSL / Example Shell	Title	Programming Notes	Deliverable [Priority]
3.7.	Safety	AE1	Summary of Treatment Emergent Adverse Events for Participants with Absolute Neutrophil Count Below Lower Value of PCI		SAC
Serious and Other Significant Adverse Events					
3.8.	Safety	AE16	Summary of Serious Treatment Emergent Adverse Events by System Organ Class and Preferred Term (Number of Participants and Occurrences)		EOT, SAC
3.9.	Safety	AE16	Summary of Fatal Serious Treatment Emergent Adverse Events by System Organ Class and Preferred Term (Number of Participants and Occurrences)	Only with subcategory: Number of Fatal SAEs	EOT, SAC
3.10.	Safety	AE1	Summary of Serious Treatment Emergent Drug-related Adverse Events by System Organ Class and Preferred Term		SAC
3.11.	Safety	AE1	Summary of Adverse Events Leading to Permanent Discontinuation of Study Treatment or Withdrawal from Study by System Organ Class and Preferred Term		EOT, SAC
3.12.	Safety	AE1	Summary of Post-treatment Serious Adverse Events by System Organ Class and Preferred Term		SAC
3.13.	Safety	AE1	Summary of Treatment Emergent Adverse Events of Special Interest by Lower Level Term		EOT, SAC
3.14.	Safety	AE1	Summary of Treatment Emergent Adverse Events of Special Interest by System Organ Class and Preferred Term		EOT, SAC
3.15.	Safety	Example 17	Summary of Post-Inhalation Cough by Visit		EOT, SAC
3.16.	Safety	Example 28	Summary of Post-Inhalation Cough by Visit and Cough Type		EOT, SAC
3.17.	Safety	Example 33	Summary of Post-Inhalation (PI) Cough at Any Visit		EOT, SAC

Safety: Tables					

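### The rule for a missing AE stop day caps the date at treatment stop regardless of AE onset or recorded month, so some AEs end before they start and others are moved out of their recorded stop month

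*SAP*

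**What the plan says.** SAP Section 13.6.2.1 allows partial AE dates with month and year recorded: "that is, the day of the month may be missing". It states the purpose of the imputation: "the following conventions will be applied for calculating the time to onset and the duration of the event".

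- **Stop day missing:** "Last day of the month will be used, unless this is after the stop date of study treatment"; if it is, "in this case the study treatment stop date will be used".
- **Start day missing:** "First of the month will be used unless this is before the start date of study treatment"; if it is, the treatment start date is used and the event is treated as on-treatment.

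Other sections bring AEs after last dose into scope. Section 13.3.3 counts an AE as treatment-emergent if its onset is "on or before treatment stop date plus 10 days". Section 13.11.8 lists Table 3.2, "Summary of Post-Treatment Adverse Events by System Organ Class and Preferred Term", and Table 3.12 for post-treatment serious AEs. Section 13.3.1 sets the period after treatment: "The 12-Week Follow-up Period is assigned from Study Day 85 to Study Day 168".

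The same imputation wording stands in all three versions of the plan in the file.

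**The concern.** A cap at treatment stop makes sense only if the event was over by then. The rule does not check this. It looks at neither the AE start date nor the recorded stop month, although both can show that the event ended after last dose.

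Two things go wrong. An AE that began after last dose is given an end date before it began. An AE that began on treatment and is recorded as ending in a later month has that recorded month overwritten. Month and year are collected data, so the rule discards information as well as filling a gap. At stake is the AE duration that the plan says these conventions serve.

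The concomitant-medication rule in the same section has no cap at treatment stop for a partial stop date, so nothing in the reporting conventions forces the AE rule to have one.

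**Working it through.** The plan gives no figure to reproduce. The check applies the rule literally.

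**Inputs**
- Imputed stop = month-end of the recorded stop month, or the treatment stop date if month-end is later (Section 13.6.2.1).
- Duration = stop − start + 1. This is an assumption. The plan gives no AE duration formula, but Section 13.5.2 counts exposure this way.
- Treatment stop at Day 84 and AE dates up to Day 168 (Section 13.3.1); full treatment is assumed.
- Calendar dates are illustrative.

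**A. Complete start date after last dose, stop day missing**

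The month-end of the stop month is on or after the AE start, and the AE start is after treatment stop. Month-end is therefore always after treatment stop, the cap always applies, and the imputed stop is before the start.

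- Randomised 10 January 2018, so Day 84 is 3 April 2018. AE start 8 April (5 days after last dose, hence treatment-emergent), stop in April: imputed stop 3 April, duration −5 + 1 = −4 days.
- Same participant, AE start 10 May, stop in May: imputed stop 3 April, duration −37 + 1 = −36 days.
- All randomisation dates in 2018, with start and true stop both between Day 85 and Day 168: 365 × (84 × 85 / 2) = 1,303,050 combinations, all with stop before start. The extreme is start on Day 168: 84 − 168 + 1 = −83 days.

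**B. Onset on treatment, recorded stop in a later month**

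- Last dose 10 March, start 1 March, stop in April: month-end 30 April is after 10 March, so the imputed stop is 10 March and the duration is 10 days. The recorded month implies 1 March to 1 April (32 days) at the shortest and 1 March to 30 April (61 days) at the longest.
- Last dose 3 April, start 25 March, stop in May: imputed duration 10 days, against 38 to 68.
- All 2018 randomisation dates with a true stop on Days 85 to 168: 365 × 84 = 30,660 combinations. In 25,287 (82%) the imputed date falls in an earlier month than the one recorded. In the other 5,373 (18%) the recorded month is the treatment-stop month, so the month is kept.

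The percentages in B depend on the assumed year and a Day 84 stop. The result in A does not.

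**C. Start day missing**

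If the recorded month is the month treatment started, moving the date to treatment start stays inside that month. If the recorded month is earlier, onset is known to precede treatment, yet the rule sets it to treatment start and so makes the event treatment-emergent under Section 13.3.3.

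**The case against.** The strongest reply is that no planned result is shown to use the faulty value. No AE table in Section 13.11.8 is titled as a duration summary. The cough displays (Tables 3.15 to 3.17) report duration in minutes, and Section 8.1.1.1 describes cough monitoring within 5 minutes of dosing, so they do not rest on AE calendar dates. Tables 3.2 and 3.12 summarise AEs by system organ class and preferred term. The treatment-emergent flag uses onset, and listings show partial dates as captured. All of this stands and limits the impact to a derived variable. It does not make the rule right, because the section says the conventions are there to calculate duration.

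Four stronger readings are tempting, and the plan does not support them.

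- **That durations are always understated.** If the recorded month is the treatment-stop month and the event really ended before last dose, the cap makes it too long: with last dose 10 March and true stop 5 March, the imputed stop is 10 March.
- **That every AE after last dose with a missing stop day ends before it starts.** If the start day is also missing and the start month is the treatment-stop month, the start is set to the first of that month, or to treatment start if that is later. No reversal then arises.
- **That pre-treatment events will be counted as treatment-emergent.** This needs an AE recorded with an onset month before the month of first dose. Section 2.2 puts the first dose within 48 hours of starting standard of care, medical history has its own tables, and the SAP does not say when AE recording begins. The point is conditional.
- **That AE collection runs to Day 168.** The SAP defines the follow-up period and lists post-treatment tables, but does not state this. The stop-day fault does not depend on it, because the 10-day window after last dose is enough.

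**Conclusion.** The stop-day rule is wrong as written, and nothing elsewhere in the plan corrects it. An AE with a complete start date after last dose and a missing stop day always gets a stop before its start. An AE recorded as ending in a month after the treatment-stop month always loses that month.

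The consequence is modest. It falls on derived AE duration only, and the number of partial dates is not known. A reader might infer that the planned safety tables are wrong; the stop-day rule does not show that. The start-day rule could affect treatment-emergent counts, but only if an AE is recorded with an onset month before the month treatment started. The day counts assume inclusive counting; the reversal of dates does not depend on it.

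**What to change.** Amend Section 13.6.2.1 so that imputation stays within the recorded month.

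- **Stop day missing:** use the last day of the recorded month, capped at the date of study completion, withdrawal or death, and never before the AE start date.
- **Start day missing:** use the treatment start date only when the recorded month is the month treatment started and the first of that month precedes treatment start; otherwise use the first of the recorded month.

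The cost is about two sentences of SAP wording and the matching change to the derivation program. No new data are needed.

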13.3.2.1. Study Phases for Concomitant Medication

Study Phase	Definition
Prior	If medication end date is not missing and is before Randomisation Date
Concomitant	Any medication that is not a prior

NOTES:

- Please refer to [Appendix 6: Reporting Standards for Missing Data](#) for handling of missing and partial dates for concomitant medication. Use the rules in this table if concomitant medication date is completely missing.

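### As written, an adverse event with no start date is not treatment emergent unless the treatment stop date is also missing, so it is left out of the treatment-emergent tables

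*SAP*

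**What the plan says.** Section 13.6.2.1 (Handling of Missing and Partial Dates) foresees adverse events with no start date at all: "Completely missing start or end dates will remain missing, with no imputation applied". The only consequence it draws is "Consequently, time to onset and duration of such events will be missing". It does not say how such an event is classified.

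Section 13.3.3 (Treatment Emergent Flag for Adverse Events) defines the flag by onset date: "If AE onset date is on or after treatment start date & on or before treatment stop date plus 10 days". Its notes contain one default for a missing date: "If the study treatment stop date is missing, then the AE will be considered to be On-Treatment". That covers the treatment stop date, not the event's onset date.

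The list of safety tables in Section 13.11.8 builds most adverse event summaries on this flag, for example Table 3.8, "Summary of Serious Treatment Emergent Adverse Events by System Organ Class and Preferred Term", and Table 3.9, "Summary of Fatal Serious Treatment Emergent Adverse Events by System Organ Class and Preferred Term".

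**The concern.** Two rules that are each reasonable combine badly. One leaves the onset date blank, and the other needs an onset date before the event can count. The result is non-conservative and goes against the plan's handling of neighbouring cases, where incomplete information tends to bring the event or medication into the on-treatment set.

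At stake is the incidence of harm by dose arm in the main safety summaries. Within the treatment-emergent tables a missing start date can only remove an event. One serious or fatal event missing from a single arm could be noticeable in a comparison across arms. If the rule is not settled in advance, whoever programs the flag must decide, possibly with the data by arm in view.

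**Working it through.** The plan states no figure on this point, so there is none to reproduce. The check is to apply the rules as written to each case and then trace the result through the displays.

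**Step 1: classification.**

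| Case | Rule | Result |
|---|---|---|
| Event start day missing; first of the month falls before treatment start | 13.6.2.1: "in this case the study treatment start date will be used and hence the event is considered On-treatment" | On-treatment |
| Event start day missing; first of the month falls on or after treatment start | 13.6.2.1: first of the month is used | The 13.3.3 test decides |
| Treatment stop date missing | Note in 13.3.3 | On-treatment |
| Concomitant medication date completely missing | 13.3.2.1: "Use the rules in this table if concomitant medication date is completely missing" | With no end date the medication cannot be prior, so it is concomitant |
| Event start date completely missing; treatment stop date known | None | Neither half of the 13.3.3 condition is met, so the event is not flagged |
| Event start date and treatment stop date both missing | Note in 13.3.3 | On-treatment |

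The fifth row is the gap.

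**Step 2: which adverse event tables depend on the flag (Section 13.11.8, Tables 3.1 to 3.14).**

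- Restricted by title to treatment-emergent events: 3.1, 3.3, 3.4, 3.5, 3.7, 3.8, 3.9, 3.10, 3.13 and 3.14. That is 10 of 14, and an undated event is absent from all of them.
- Post-treatment: 3.2 and 3.12. Appendix 3 defines no post-treatment flag. If the programmed rule is onset later than ten days after treatment stop, the undated event is excluded. If it is every event not flagged treatment emergent, the event is included. The result is undetermined.
- No timing restriction in the title: 3.6 (all events by maximum intensity) and 3.11 (events leading to discontinuation or withdrawal). The event is in 3.6, and in 3.11 if applicable.

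The counts add up: 10 + 2 + 2 = 14.

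**Step 3: by deliverable.** Seven of the ten affected tables (3.1, 3.3, 3.4, 3.8, 3.9, 3.13, 3.14) are produced at the End of Treatment interim as well as at the final analysis. The other three (3.5, 3.7, 3.10) are final only: 7 + 3 = 10. Table 3.6 and Listings 13, 16 and 17 are also final only. At the End of Treatment interim, Table 3.11 is therefore the only one of Tables 3.1 to 3.14 that could show an undated event, and only if the event led to discontinuation or withdrawal. At the final analysis the event is in Table 3.6, Listing 13, and Listing 16 or 17 if serious.

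**Step 4: size.** The plan does not say how often a start date is completely missing. As an illustration only, if the share were 0.5% to 2% (an assumption with no basis in the document), 200 events would include 200 × 0.005 = 1 to 200 × 0.02 = 4 such events.

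**The case against.** The strongest case against is that the exclusion comes from silence, not from a stated rule. Section 13.6.2.1 presents its conventions as serving the calculation of onset time and duration, and never says that an undated event goes unflagged. Section 8.1 bases adverse event analyses on the sponsor's data standards, which are not shown and may hold a default. The case is also probably rare: Section 13.6.2.1 describes partial dates as lacking only the day, and the final analysis follows database cleaning. Nothing in the document suggests that serious events or deaths would lack a start date.

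The point about frequency stands and limits the size of the problem. The point about unseen standards stands in part: a default may exist there, but the SAP writes its own flag and its own date rules and points to none for this case.

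A reader might be tempted by three stronger readings, which the document does not support:

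- *The event also drops out of the post-treatment tables.* The plan never defines post-treatment, so this cannot be concluded.
- *Every undated event fails the flag.* The note on a missing treatment stop date is an exception.
- *Undated serious or fatal events disappear from the safety report.* At the final analysis they remain in Table 3.6, in Table 3.11 where applicable, and in Listings 13, 16 and 17. Section 8.4 summarises all-cause mortality by treatment, which does not depend on an event's onset date. Post-inhalation cough seen at clinic visits is summarised whether or not it was also reported as an adverse event (Section 8.1.1.1).

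Nor do partial start dates always default to on-treatment. That happens only when the first of the month falls before treatment start.

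**Conclusion.** The concern holds in limited form. Followed as written, Sections 13.3.3 and 13.6.2.1 leave an adverse event with no start date outside the treatment-emergent set whenever the treatment stop date is known, and so outside ten tables that include the serious, fatal and special-interest summaries. In those tables the bias is towards under-reporting harm, and it is inconsistent with the plan's defaults for a missing treatment stop date and for missing medication dates. Treatment in Tables 3.2 and 3.12 is undetermined.

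The number of events is unknown and likely small, and efficacy is not affected. The conclusion assumes that no unseen sponsor standard supplies a default and that the flag is programmed literally. The gap still deserves correction, because the plan itself foresees these events and the remedy is short.

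**What to change.** Add to the notes in Section 13.3.3 that an adverse event with a completely missing start date is counted as treatment emergent unless its known stop date precedes the first dose. In the same section, define post-treatment as onset later than ten days after treatment stop, so that Tables 3.2 and 3.12 have a stated basis. Leave time to onset and duration missing for these events, as Section 13.6.2.1 now provides.

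The cost is a short addition to the SAP and one condition in the flag program. The downside is that a few events that in fact began before or after treatment may be counted as treatment emergent. That is a conservative error, in keeping with the plan's other defaults.

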13.7. Appendix 7: Values of Potential Clinical Importance

13.7.1. Laboratory Values

Haematology				
Laboratory Parameter	Units	Category	Clinical Concern Range	
			Low Flag (< x)	High Flag (>x)
Haemoglobin	G/DL	Male 18-64 years	7.1	19.9
		Male 65+ years	7.1	19.9
		Female 18-64 years	7.1	19.9
		Female 65+ years	7.1	19.9
Lymphocytes	GI/L		0.85	4.1
Total Absolute Neutrophil Count	GI/L		1.5	8
Platelet Count	GI/L		31	1499
White Blood Cell count	GI/L	18-64 years	1.1	10.8
		65+ years	1.1	10.8

Clinical Chemistry				
Laboratory Parameter	Units	Category	Clinical Concern Range	
			Low Flag (< x)	High Flag (>x)
Albumin	g/L		32	50
Calcium	mmol/L		1.5	3.24
Creatinine		Male 40-49 years	69	160
		Male 50-59 years	67.2	160
		Male 60-69 years	67.2	160
		Male 70+ years	59.2	160
		Female 40-49 years	52.2	160
		Female 50-59 years	53	160
		Female 60-69 years	53	160
		Female 70+ years	55.7	160
Glucose	mmol/L	13-49 years	2.2	27.8
		50+ years	2.2	27.8
Potassium	mmol/L		2.8	6.5
Sodium	mmol/L		120	160
Urea/BUN	mmol/L	13-64 years	2.5	15
		65+ years	2.5	15

Liver Function			
Test Analyte	Units	Category	Clinical Concern Range
ALT/SGPT	U/L	High	≥ 2x ULN
AST/SGOT	U/L	High	≥ 2x ULN
AlkPhos	U/L	High	≥ 2x ULN
T Bilirubin	μmol/L	High	≥ 2x ULN
T. Bilirubin + ALT	μmol/L U/L	High	2xULN T.Bilirubin + ≥ 3x ULN ALT
Direct Bilirubin	μmol/L		0 – 6

13.7.2. ECG

ECG Parameter	Units	Clinical Concern Range	
		Lower	Upper
Absolute			
Absolute QTc Interval	msec		> 530
Absolute PR Interval	msec	< 110	> 240
Absolute QRS Interval	msec	< 75	> 110
Change from Baseline			
Increase from Baseline QTc	msec		> 60

13.7.3. Vital Signs

Vital Sign Parameter (Absolute)	Units	Clinical Concern Range	
		Lower	Upper
Systolic Blood Pressure	mmHg	< 95	> 160
Diastolic Blood Pressure	mmHg	< 55	> 100
Heart Rate	bpm	< 40	> 110

13.8. Appendix 8: Population Pharmacokinetic (PopPK) Analyses

13.8.1. Population Pharmacokinetic (PopPK) Methodology

All analysis will be performed in the validated Modelling and Analysis Platform (MAP). MAP consists of a Linux desktop containing various modelling applications, including NONMEM, PsN, Pirana, R and RStudio. All software versions used will be documented.

The population PK analysis will be performed in the following sequence of steps:

1. Exploratory data analysis/data check out.
2. Base structural model development.
3. Covariate analysis.
4. Model refinement.
5. Model evaluation.
6. Model application using simulation

The above analysis and reporting steps follow EMEA (http://www.ema.europa.eu/docs/en_GB/document_library/Scientific_guideline/2009/09/WC500003067.pdf) and FDA population PK guidances (<https://www.fda.gov/downloads/drugs/guidances/UCM072137.pdf>)

Key components of these regulatory guidelines on population PK are also included in the Global CPMS guidance for pop pk RAP (<https://connect.gsk.com/sites/cpms/TandD/Guidances>).

